6.7.7.8. Attack Symptoms

Symptoms reported for adjusted attacks will be included in summaries of attack characteristics. In addition, listings of diary data will show symptoms for all subject reported attacks.

6.7.7.9. Attack Location

The anatomical location of each subject-reported and adjusted attack will be determined based on the symptoms indicated in the diary as shown in Table 3.

Table 3: Determination of Attack Location Using Symptoms Collected in the Diary

Abdominal-Only Attack	Mixed Attack	Non-abdominal Attack (Inclusive of Skin and Airway Swelling)

Symptoms checked must only come from this box:
 
Internal swelling or symptoms of internal swelling in the abdomen:
 
 Nausea Abdominal discomfort Cramps (colicky pain) Vomiting Abdominal pain Diarrhea 	
Must have at least 1 symptom from left and right box (from abdominal and non-abdominal attack characterization)
	
Symptoms checked must only come from this box:
 
Peripheral (Non-laryngeal) Events:
 
Visible swelling:
 
 face/head neck (outer swelling) legs buttocks/genitals eyes arms feet stomach (outside) hands chest/back joints

Abdominal-Only Attack	Mixed Attack	Non-abdominal Attack (Inclusive of Skin and Airway Swelling)
		
Pink rings (erythema marginatum) with other swelling
 
Laryngeal Events:
 
Internal swelling or symptoms of internal swelling of the airways:
 
 mouth/tongue/lips lump in throat/tightness change in voice difficulty swallowing difficulty breathing

Note: Symptoms of headache and substantial fatigue may be checked by the subject but play no role in the characterization of the location of a subject-reported attack.

6.7.7.10. Laryngeal Events

Laryngeal events are those events that have visible swelling in the mouth/tongue/lips or any of the following internal swelling symptoms: lump in throat (tightness), change in voice, difficulty swallowing, or difficulty breathing, as recorded in the subject diary. Note that swelling of the lips may not indicate a true laryngeal event but is an artifact of the data collection tool.

6.7.7.11. Peripheral (non-abdominal, non-laryngeal) Events

Peripheral events are those events that have visible swelling of the face/head, neck (outer swelling), legs, buttocks/genitals, eyes, arms, feet, stomach (outside), hands, chest/back, and joints. This also includes erythema marginatum (pink rings) in the presence of any other swelling.

6.7.7.12. Attack Triggers

Attack triggers for adjusted attacks will be summarized with the attack characteristics for adjusted attacks. In addition, attack triggers for each subject-reported attack will be included in the listings.

6.7.7.13. Average Number of Hospitalizations and Clinic Visits Due to HAE

The average number of hospitalizations due to HAE is derived as the number of hospitalizations due to HAE divided by the duration of the reporting period of interest. The calculation will be performed similarly to the calculation of the attack rate (see Section 6.7.7.4).

The average number of clinic visits due to HAE is derived as the number of clinic visits due to HAE divided by the duration of the reporting period of interest. The calculation will be performed similarly to the calculation of the attack rate (see Section 6.7.7.4).

6.7.8. Age at Time of Adverse Events

Age at time of AE is calculated as age at screening date plus the difference in years between screening date and the AE date, rounded down to the nearest whole number.

6.8. Presentation of Visits

For by visit displays, scheduled visits will be summarized nominally as collected on the case report form (see Table 4); unscheduled and early termination visits will not be analyzed. Data captured from unscheduled and early termination visits will be utilized in the determination of baseline values and worst post-baseline assessments. All visits will be displayed in the listings.

Table 4: Visit Windows (Days)

Visit Description	Relative Target Day	Protocol-Specified Visit Window	Analysis Visit Window
Screening visit	-84	-88 to -80	-88 ^a to -80
SOC period	-88 to -1	-88 to -1	-88 ^a to -1
Baseline visit	1	1	1
Week 2 (Day 15)	15	15 - 19	2 - 29
Week 6 (Day 43)	43	40 - 46	30 - 54
Week 9 (Day 64)*	64	57 - 71	55 - 75
Week 12 (Day 85)	85	82 - 88	76 - 99
Week 16 (Day 113)*	113	106 - 120	100 - 127
Week 20 (Day 141)*	141	134 - 148	128 - 155
Week 24 (Day 169)	169	162 - 176	156 - 183
Week 28 (Day 196)*	196	189 - 203	184 - 210
Week 32 (Day 225)*	225	218 - 232	211 - 239
Week 36 (Day 253)	253	246 - 260	240 - 267
Week 40 (Day 281)*	281	274 - 288	268 - 295
Week 44 (Day 309)*	309	302 - 316	296 - 323
Week 48 (Day 337)	337	330 - 344	324 - 379
Week 60 (Day 421)*	421	414 - 428	380 - 463
Week 72 (Day 505)	505	498 - 512	464 - 547
Week 84 (Day 589)*	589	582 - 596	548 - 631
Week 96 (Day 673)	673	666 - 680	632 - 715
Week 108 (Day 757)*	757	750 - 764	716 - 799
Week 120 (Day 841)	841	834 - 848	800 - 883
Week 132 (Day 925)*	925	918 - 932	884 - 967
Week 144 (Day 1009)	1009	1002 - 1016	≥ 968

Abbreviation: SOC = standard of care.

Weeks with * will have telephone call or telemedicine visit.

^a-88 days or earlier if the informed consent date is prior to day -88; this day is relative to the day the first dose of study drug is given.

In certain presentations, the HAE attack rates are summarized by month. The HAE attack will be assigned to an analysis month according to the study day of the actual HAE attack using the following conventions in Table 5:

Table 5: Attack Days Windows (Days)

Attack Day	Analysis Month for Display*
Date/Time of Consent to -1	SOC or Baseline
1 – 28	Month 1 (Day 1 – 28)
29 – 56	Month 2 (Day 29 – 56)
57 – 84	Month 3 (Day 57 – 84)
85-1112	Month 4 (Day 85-112)
113-140	Month 5 (Day 113-140)
141-168	Month 6 (Day 141-168)
169-196	Month 7 (Day 169-196)
197-224	Month 8 (Day 197-224)
225-252	Month 9 (Day 225-252)
253-280	Month 10 (Day 253-280)
281-308	Month 11 (Day 281-308)
309 to Week 48 visit	Month 12 (Day 309 to Week 48 visit)

Abbreviation: SOC = standard of care.

*28-day month blocks through the end of Part 2 (Week 48 visit) of the study. The values in “()” may or may not be used on the actual display depending on space availability.

Note that an attack on Day 1 with the time recorded prior to the first dose of berotralstat will be included in the SOC period. Alternatively, an attack on Day 1 with the time after the first dose of berotralstat or an attack with no time will be included as an on-study attack starting on Day 1. Also note that since effectiveness data are only to be collected through the end of Part 2 (Week 48 visit); an attack that falls beyond Day 336 will be included in Week 48 (Month 12).

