10.4. Weight/Height/Body Mass Index

Subject weight is important for this study as the dose of berotralstat will be based on subject weight. Therefore, the site should be diligent in accurately taking and recording subject weight. Subjects should be weighed in light clothing with shoes and other heavier items (eg, belts or phones) removed. Heavier outer clothing (eg, jackets or sweaters) should also be removed.

Height should be recorded at the indicated visits. Body mass index (BMI) should be calculated at all visits where weight and height are measured using the following formula:

$$\text{BMI} = \text{weight (kg)} / \text{height (m)}^2$$

10.5. 12-lead Electrocardiograms

A standard bedside or routine 12-lead ECG machine that calculates heart rate and measures the PR, QRS, QT, RR, and QTc intervals will be used. Prior to obtaining an ECG, subjects should rest quietly for at least 10 minutes. Resting may be in a supine position or other position (eg, on the P/C's lap) as age appropriate for the subject.

Qualified site personnel should review the ECGs and automated findings in real time for gross abnormalities and interval measurements of concern (absolute readings and for post-baseline ECGs, a change from baseline). For all ECGs, the clinical interpretation of the ECG and calculated QTc should be recorded directly on a hard copy of the ECGs. Copies of the ECGs may be requested by the sponsor. All subject identifiers will be masked prior to provision to the sponsor.

Baseline (pre-dose) ECGs will be obtained in triplicate (ie, 3 separate readings taken at 1- to 5-minute intervals) with baseline values calculated from an average of the 3 readings. All other ECGs will be single assessments.

An ECG should be repeated for a change from baseline in QTc > 60 msec or a QTc interval > 500 msec.

If AEs commonly associated with prolonged QTc interval (eg, unexplained intermittent or continuous lightheadedness, syncope, palpitation, chest pain) are reported or the dose is modified, additional ECGs should be recorded. ECGs obtained due to dose modification should be taken approximately 2 to 6 weeks after dose modification and should be aligned with PK blood sample timelines described in Section 10.9.1 to the extent possible.

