6.4. Data Presentation Conventions

Continuous data will be summarized using the number of subjects with available data, mean, standard deviation (SD) or standard error of the mean (SEM), median, minimum, and maximum. Categorical data will be summarized using counts/frequencies and percentages. Percentages will be calculated using the total number of subjects per cohort unless otherwise specified.

Means and medians will be formatted to 1 more decimal place than the measured value, SDs and SEMs to 2 more decimal places, and minimum and maximum values to the same number of decimal places. For categorical variables, the number and percentage of responses will be presented in the form XX (XX.X%) where the percentage is in the parentheses, except that 100% will be presented to 3 digits with no decimal. Adverse event data will be presented in the form XX (XX.X%) [XXX] where the number of subjects with at least 1 event (incidence) is the first number and the number of occurrences of an event is in “[]”. Dates will be formatted as DDMMYYYY and times will be formatted in 24-hour time as HH:MM. Partial dates will be handled as described in Section 8.5.

Berotrastat concentration data will be listed and summarized as part of the statistical analysis for this study and included in the Clinical Study Report. Noncompartmental PK parameters will be calculated as described in Section 10.1.2 and included in the Clinical Study Report. PK parameters from population PK modeling will be calculated and summarized as described in the Population PK Analysis Plan and included in the Population PK report.

Wherever possible, data will be decimal aligned.

A table of contents at the end of this SAP provides the expected titles and numbers of the tables, listings, and figures of the final report. Changes to titles or numbering in the final report will not necessitate a revision to the SAP, nor will they be considered deviations from planned analyses. Additional data listings supporting the tables will not be considered a deviation from planned analyses.

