6.8.1. Multiple Assessments

Where multiple scheduled measurements are recorded for a given time point (ie, triplicate ECGs or repeated blood pressure assessments), the mean of the measurements will be calculated and used in any derivation of summary statistics. All available data will be listed.

When multiple visits occur within the same window, the scheduled visit will be used in the analysis if available. If no scheduled visit occurs within the window and unscheduled visit(s) and/or an early termination visit occur within the window, the analysis visit closest to the target day will be selected for use in analysis. If deemed appropriate by the sponsor (eg, in the case of a

retest), unscheduled visits may be chosen for analysis given documentation of the desired visit from the sponsor.

Results from unscheduled visits will be eligible for inclusion in analyses of worst post-baseline results regardless of their use for 'by visit' displays.

Listings will display all visits as recorded on the eCRF, including the date and study day. All available data including any totals, domains, or subscales of scale assessments summarized will be listed.

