8.6. Values of Clinical Concern

QTcF intervals >500 msec or a change from baseline in QTcF > 60 msec and a simultaneous absolute QTcF > 460 msec are of clinical concern.

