11.5. ECGs

A standard bedside or routine 12-lead ECG will be obtained as scheduled in Table 2. Baseline (pre-dose) ECGs will be obtained in triplicate and all other ECGs will be single assessments. For the purposes of deriving baseline values, any triplicate ECGs collected prior to dosing on Day 1 will be averaged, by using the arithmetic mean.

Descriptive summaries of ECG parameters (PR, QRS, QT, QTc, QTcF, QTcB, RR, heart rate) will be presented by parameter, time point, and cohort. ECG interpretations (normal, abnormal, abnormal clinically significant) will be presented by time point and cohort.

The number and percentage of subjects with QTcF values will be summarized by category for ranges (≤ 450 , >450 and ≤ 470 , >470 and ≤ 500 , and > 500 msec) and increase-from-baseline ranges (< 30 , 30 to 60, and > 60 msec) by time point and treatment group. In addition, QTcF and PR change over time will be plotted over time.

ECG results will be listed by cohort, subject, parameter, and time point.

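### No planned QTcF category summary takes in unscheduled ECGs or counts subjects who ever met the SAP's own QTcF criterion; the visit-selection rules conflict, and the default denominator dilutes by-visit percentages

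*SAP*

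**What the plan says.** **What is tabulated.** SAP 11.5: "The number and percentage of subjects with QTcF values will be summarized by category for ranges" of absolute QTcF (cuts at 450, 470 and 500 msec) and of increase from baseline (cuts at 30 and 60 msec), "by time point and treatment group". Table 7 lists this as output 14.3.5.1.3. Neither place mentions a worst or any post-baseline QTcF category.

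**Which visits count.** SAP 6.8 says of by-visit displays that "unscheduled and early termination visits will not be analyzed". Its next sentence reads: "Data captured from unscheduled and early termination visits will be utilized in the determination of baseline values and worst post-baseline assessments". SAP 6.8.1 differs. If a window has no scheduled visit but does contain unscheduled or early termination visits, "the analysis visit closest to the target day will be selected for use in analysis". It also lets the sponsor select an unscheduled visit, with a retest as the example.

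**Denominator.** SAP 6.4: "Percentages will be calculated using the total number of subjects per cohort unless otherwise specified". SAP 11.5 states no exception.

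**The plan's own threshold.** SAP 8.6 singles out "QTcF intervals >500 msec or a change from baseline in QTcF > 60 msec and a simultaneous absolute QTcF > 460 msec".

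**When extra ECGs are taken.** Protocol 10.5 asks for a repeat when QTc exceeds 500 msec or rises by more than 60 msec, and for additional ECGs when symptoms associated with QT prolongation are reported or the dose is modified. On timing: "ECGs obtained due to dose modification should be taken approximately 2 to 6 weeks after dose modification". The schedule of assessments (Protocol Table 2) has post-baseline ECGs at Weeks 2, 6, 12, 24, 36, 48 and 144 and at the end-of-study visit.

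**The concern.** Protocol 4.4.5 notes a labelled precaution for QT prolongation at dosages above the recommended 150 mg daily. Doses here are weight-banded and may change with weight throughout Parts 2 and 3. ECGs prompted by symptoms or by a dose change are therefore among the most informative in the study, and they are the ones most likely to be unscheduled.

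SAP 6.8 sends such ECGs to worst-post-baseline assessments, but for QTcF categories there is no such output to receive them. Laboratory data are treated differently: SAP 11.3.1 and Tables 14.3.4.4.1 to 14.3.4.4.3 summarise shifts to the worst post-baseline grade. The category table could thus show no prolonged value in a row although a child had one. By-visit rows also cannot be added up to give the number of children ever affected, because one child can appear at several visits.

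**Working it through.** **1. Stated figures.** The documents give no expected QTcF rate. The only design probability is the chance of seeing at least one case of an event with a 10% rate in 30 subjects: 1 − 0.9^30 = 0.958, which agrees with the stated 96% and is not in dispute.

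**2. Where a dose-change ECG falls.** Assume the dose changes on a visit's target day and the ECG follows 14 to 42 days later, a span of 29 days. Compare with the analysis windows in SAP Table 4.

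| Change at (target day) | ECG due, days | Analysis window | ECG on the schedule there? |
|---|---|---|---|
| Week 12 (85) | 99–127 | Week 12: 1 day; Week 16: 28 | Week 16: no (tele-contact) |
| Week 24 (169) | 183–211 | Week 24: 1; Week 28: 27; Week 32: 1 | Weeks 28, 32: no (tele-contact) |
| Week 36 (253) | 267–295 | Week 36: 1; Week 40: 28 | Week 40: no (tele-contact) |
| Week 48 (337) | 351–379 | Week 48 (324–379): all 29 | Yes, at the visit where the dose changed |
| Week 72 (505) | 519–547 | Week 72 (464–547): all 29 | No |
| Week 96 (673) | 687–715 | Week 96 (632–715): all 29 | No |
| Week 120 (841) | 855–883 | Week 120 (800–883): all 29 | No |

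An early change is better covered. For a change on Day 15 the span is Days 29–57. Of these, 25 days lie in the Week 6 window, and the scheduled Week 6 ECG (Day 43) is itself taken four weeks after the change.

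**3. Apply the two visit rules.**
- Under 6.8, every unscheduled ECG in the table above is left out of the by-visit display.
- Under 6.8.1, for a change at Week 48, the scheduled Week 48 visit takes precedence, so the value shown predates the new dose unless the sponsor selects the later ECG.
- Under 6.8.1, for changes at Weeks 72, 96 and 120, the outcome depends on how the rule is read. Applied per visit, the scheduled visit wins and has no ECG. Applied per assessment, the unscheduled ECG is used. The same ambiguity affects the tele-contact windows.

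**4. Can the 8.6 criterion be read from the table?** Values above 500 msec have their own row at each visit. Any child with an increase above 60 msec and a simultaneous QTcF above 460 msec is in the >60 row at that visit, but so is any child with the increase alone. There is no cut at 460 and no cross-classification, so the joint condition cannot be separated, and no row covers the whole treatment period.

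**5. Denominator.** Displayed percentage = events / total N; percentage among those assessed = events / assessed. The dilution factor is assessed / total N. Take N = 30 (the planned total). The numbers assessed are assumptions. Fifteen is the minimum number completing Week 48 in Protocol 7.1 and the trigger for the first interim analysis in SAP 5.1.

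| Assessed | Factor | One child >500 msec: displayed | Among assessed |
|---|---|---|---|
| 30 | 1.00 | 3.3% | 3.3% |
| 25 | 25/30 = 0.83 | 3.3% | 1/25 = 4.0% |
| 20 | 20/30 = 0.67 | 3.3% | 1/20 = 5.0% |
| 15 | 15/30 = 0.50 | 3.3% | 1/15 = 6.7% |

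In a cohort at the minimum size of 4, one child is displayed as 25%, against 33% with 3 assessed and 50% with 2.

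**The case against.** The strongest reply is that QTcF reporting does not rest on this one table. Listing 16.2.8.4 covers the 12-lead ECGs, and the SAP says listings display all visits. Figure 14.3.5.3.1.3 plots QTcF changes for all observations. Table 14.3.1.14 covers events in the torsade/QT query. Adverse events leading to interruption or discontinuation are tabulated, and dose changes are listed. With about 30 children and no inference, individual listings carry real weight. This stands, and it limits the point to the categorical summary.

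A reader might infer more than the documents support:

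- *That QTcF prolongation will be under-reported overall.* The other outputs remain, and attrition, dose-change frequency and QTcF rates are not given, so no amount can be computed.
- *That any triggered ECG is lost.* A repeat that confirms a prolonged scheduled ECG hides nothing if omitted, because the first value is already counted. SAP 6.8.1 also lets the sponsor choose an unscheduled visit. That is discretion rather than a pre-specified rule, but it means exclusion is not absolute.
- *That there are no protocol-required ECGs between Weeks 48 and 144.* Children who leave in Part 3 complete the Week 144 assessments (Protocol 9.5.3) and have end-of-study assessments. Dose-change ECGs are aligned with PK sampling where possible, and for weight-based changes that sampling may move to the next visit. SAP 6.8 summarises visits as recorded on the case report form, so some of these ECGs may sit under a scheduled visit. The documents do not settle this.
- *That the table cannot show the 8.6 criterion at all.* The >500 and >60 rows contain every child who meets it at that visit; the joint row and the whole-period count are what is missing.
- *That cases disappear through the denominator.* Counts are printed and are unaffected. SAP 6.2 asks tables to show the number of subjects to which the data apply, and the shells, in a separate document not available here, may set another denominator.

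**Conclusion.** The point holds for the QTcF category table. As written, SAP 6.8, 11.5 and Table 7 allow a prolonged QTcF seen only on a symptom-triggered or dose-change ECG to be absent from Table 14.3.5.1.3, and they plan no table of children who ever met the 8.6 criterion. The exposure is greatest after Week 48, given the gap in scheduled ECGs at Weeks 72, 96 and 120. Separately, 6.8 and 6.8.1 give different answers for the same unscheduled ECG and must be reconciled.

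The effect on the category table for one affected child is a count of 0 where an any-post-baseline row would show 1. The denominator effect is a factor of 0.83 to 0.50 for 25 to 15 of 30 assessed. It applies to percentages only and assumes that the shells do not override SAP 6.4. The window mapping assumes that dose changes occur on target days. The documents do not support a statement about how often any of this will happen.

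**What to change.** 1. Add to SAP 11.5 and Table 14.3.5.1.3 an any/worst-post-baseline section that uses all post-baseline ECGs, including unscheduled and early termination ones. Keep the existing categories and add a row for the joint 8.6 condition (increase above 60 msec with simultaneous QTcF above 460 msec).
2. Rewrite 6.8 and 6.8.1 as one pre-specified visit-selection rule. State whether it operates per visit or per assessment, and whether a tele-contact counts as a scheduled visit for this purpose.
3. For by-visit categorical tables, set the denominator to subjects with a non-missing assessment at that visit and, for change categories, a baseline value as well.

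The cost is SAP wording, a few more rows in one table, and percentages that may look less favourable. The data are already collected. The ECG schedule, dosing and stopping criteria are untouched.

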6.8.1. Multiple Assessments

Where multiple scheduled measurements are recorded for a given time point (ie, triplicate ECGs or repeated blood pressure assessments), the mean of the measurements will be calculated and used in any derivation of summary statistics. All available data will be listed.

When multiple visits occur within the same window, the scheduled visit will be used in the analysis if available. If no scheduled visit occurs within the window and unscheduled visit(s) and/or an early termination visit occur within the window, the analysis visit closest to the target day will be selected for use in analysis. If deemed appropriate by the sponsor (eg, in the case of a

retest), unscheduled visits may be chosen for analysis given documentation of the desired visit from the sponsor.

Results from unscheduled visits will be eligible for inclusion in analyses of worst post-baseline results regardless of their use for 'by visit' displays.

Listings will display all visits as recorded on the eCRF, including the date and study day. All available data including any totals, domains, or subscales of scale assessments summarized will be listed.

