7.3. Subject Withdrawal from the Study and from Study Drug

7.3.1. Subject Withdrawal from the Study

Participation in the study is strictly voluntary; the parents and/or caregivers (P/C) may withdraw consent for their child or, where appropriate, the child may withdraw assent to contribute additional study information at any point. A subject who has had consent withdrawn by the P/C or assent withdrawn will be requested to attend an early termination visit to complete all end-of-study evaluations as appropriate for the study part. Although a subject may be withdrawn from the study at any time without specifying a reason for withdrawal, if known, the reason for withdrawal will be recorded in the subject's medical records (source documents) and in the case report form (CRF). If the reason for subject withdrawal is not known, the subject must be contacted to establish whether the reason was an AE, and if so, this must be reported in accordance with the procedures outlined in Section 11. If at any point in the study the clinic is unable to contact the P/C after appropriate attempts have been made, the subject will be considered lost to follow-up.

Once subjects have withdrawn from the study, the sponsor will no longer provide treatment through the study. Following withdrawal from the study, a subject will be able to receive further treatment as recommended by their treating physician and according to the accepted SOC.

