9.5.3. Week 144 / End of Treatment (EOT)

Subjects will return to the clinic for the EOT visit at Week 144 (± 1 week). Any subject who discontinues the study during Part 3 should return to the site as soon as possible to complete the Week 144 (EOT) assessments.

If an AE is ongoing at the last study visit, additional clinic visit(s) or telephone contact(s) may be warranted (see Section 11.1.1.4).

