9.6. End-of-Study (EOS) Follow-up Visit

Subjects who discontinue berotralstat either at the Week 144 visit or earlier will be required to attend a follow-up visit 3 weeks (21 ± 3 days) after study drug discontinuation. Subjects will be discontinued from the study at this visit. Subjects who discontinue the study but will continue to receive berotralstat via another mechanism will have end-of-study assessments performed at their last regularly scheduled visit. After Week 48, subjects who discontinue study drug but continue to receive berotralstat via another mechanism will be considered completers.

If an AE is ongoing at the EOS visit, additional clinic visit(s) or telephone contact(s) may be warranted (see Section 11.1.2.1).

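### SAP 6.8 and 6.8.1 conflict on early termination visits and neither sets an on-treatment limit, so an off-drug ECG or laboratory result could be summarised as a treatment week

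*SAP*

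**What the plan says.** SAP 6.8 (Presentation of Visits) summarises scheduled visits under their nominal case report form label and adds that "unscheduled and early termination visits will not be analyzed". It gives those visits a limited use: "Data captured from unscheduled and early termination visits will be utilized in the determination of baseline values and worst post-baseline assessments".

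SAP 6.8.1 (Multiple Assessments) prefers the scheduled visit when several fall in one window, then sets a fallback: "If no scheduled visit occurs within the window and unscheduled visit(s) and/or an early termination visit occur within the window", the visit closest to the target day is selected. It also lets the sponsor choose an unscheduled visit if the choice is documented.

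SAP Table 4 assigns analysis windows that run without a gap from Day 2 to Day 968 and beyond. It has no row for EOS or for early termination.

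The protocol describes three kinds of visit at or after stopping:

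- Protocol 9.6 requires a "follow-up visit 3 weeks (21 ± 3 days) after study drug discontinuation". The exception is children who "will continue to receive berotralstat via another mechanism will have end-of-study assessments performed at their last regularly scheduled visit".
- Protocol 9.5.3 adds a prompt return for end-of-treatment assessments, but only in Part 3: "Any subject who discontinues the study during Part 3 should return to the site as soon as possible".
- Protocol 7.3.1 says a child whose consent or assent is withdrawn "will be requested to attend an early termination visit to complete all end-of-study evaluations as appropriate for the study part", with no timing.

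The Schedule of Assessments includes ECG, chemistry, hematology and vital signs at the EOS visit.

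**The concern.** A programmer cannot follow both SAP sections for the same table. 6.8.1 does concern by-visit tables: it closes by making unscheduled results eligible for worst post-baseline analyses whether or not they were used in the by-visit displays.

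The choice matters because neither section tests whether the child was still taking berotralstat. With contiguous windows and no follow-up row, any visit after the last dose lands in a window labelled as a treatment week. The children concerned are those who stopped, and some may have stopped for a QTcF or liver finding. If their off-drug values enter a treatment-week row, that row no longer describes the drug. The minimum cohort sizes are 4, 4, 4 and 3, so one child can be 25% to 33% of a cohort's row.

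The SAP handles this elsewhere. Attack rates end at the last day of treatment + 1 (SAP 6.7.7.4), and adverse events are split into pre-treatment, treatment-emergent and post-treatment (SAP 11.1). By-visit ECG, laboratory and vital-sign summaries have no equivalent.

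**Working it through.** The plan gives no figure on this point. Its one computed figure, the 96% chance of seeing at least one event of 10% frequency in 30 children, reproduces (1 − 0.9^30 = 0.9576) and plays no part here.

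**Step 1. Inputs.** The EOS visit is 21 days after the last dose (range 18 to 24; Protocol 9.6). Analysis windows and target days are from SAP Table 4. Weeks 9, 16, 20, 28, 32, 40 and 44 are tele-contacts with no ECG or laboratory test scheduled. Last-dose days 1 to 84 are taken as Part 1 and 85 to 336 as Part 2.

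**Step 2. Rule applied.** Suppose that 6.8.1 governs and that EOS is handled as an early termination visit. EOS day = last-dose day + 21. The result fills an otherwise empty clinic window if that day lies in a clinic window whose target day is after the last dose.

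| Clinic window (analysis days) | Last-dose days that place EOS in it | Number of days |
|---|---|---|
| Week 2 (2–29) | 1–8 | 8 |
| Week 6 (30–54) | 9–33 | 25 |
| Week 12 (76–99) | 55–78 | 24 |
| Week 24 (156–183) | 135–162 | 28 |
| Week 36 (240–267) | 219–246 | 28 |
| Week 48 (324–379) | 303–336 | 34 |

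- Part 1: 8 + 25 + 24 = 57 of 84 (67.9%).
- Part 2: 28 + 28 + 34 = 90 of 252 (35.7%).
- Together: 147 of 336 (43.8%). The other 189 days (56.2%) fall in tele-contact windows.
- With an 18-day gap: Part 1 60, Part 2 87, total 147. With a 24-day gap: 54, 93, total 147.

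As an example, a last dose on Day 64 gives EOS on Day 64 + 21 = 85, the Week 12 target day.

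**Step 3. Sensitivity to early visits.** A scheduled visit may take place before its target day. In the table, the last dose reaches the start of the protocol visit window only on Day 162 (Week 24), Day 246 (Week 36) and Days 330–336 (Week 48), which is 1 + 1 + 7 = 9 days. If all those visits had already occurred, the total would be 147 − 9 = 138, and Part 1 would be unchanged.

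**Step 4. The other rule.** If 6.8 governs, early termination visits are left out of by-visit displays and the count is 0.

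**Step 5. Size in one row (assumed values).** Take a cohort of four in Week 12. Three children have a QTcF change of +20 msec. One stopped on Day 64 and is at 0 when off drug.

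- Off-drug value admitted: (20 + 20 + 20 + 0)/4 = +15 msec, n=4; above 60 msec, 0/4.
- Restricted to last dose + 1 day: the stopper's data end on Day 65, before the window opens on Day 76, so (20 + 20 + 20)/3 = +20 msec, n=3; above 60 msec, 0/3.

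Whatever the stopper showed on drug stays in the week in which it was measured.

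**Step 6. Which outputs are exposed.** Laboratory shifts use the worst post-baseline grade, and liver elevations count any post-baseline occurrence (SAP 11.3.1), so a later value cannot replace a worse one. For ECG, SAP 11.5 gives the QTcF categories by time point, and SAP Table 7 lists no worst-post-baseline ECG table.

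**The case against.** The strongest reply is that 6.8 already answers the question. It excludes these visits outright and summarises scheduled visits under their nominal label. EOS has its own post-treatment column in the Schedule of Assessments, and the early termination visit in Protocol 7.3.1 is a separate, untimed visit tied to withdrawal of consent or assent. On that reading no off-drug value enters a treatment week. This stands as one tenable reading, but 6.8.1 contradicts it for the same displays. The terms also overlap: Protocol 7.3.1 has the early termination visit complete the end-of-study evaluations, and Protocol 10.11 sends withdrawing children to an EOS visit.

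The second reply is that little is lost. Worst-case laboratory tables, a QTcF distribution plot over all observations, and listings with date and study day all keep the on-drug values. QTcF and liver findings that lead to stopping must be confirmed or repeated, so they are normally recorded before the child stops. This also stands, and it confines the effect to by-visit summaries.

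A reader might infer four stronger things, which the documents do not support:

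- That off-drug values will be reported as on-treatment. Only one of two conflicting rules would allow it.
- That these values have recovered. The documents give no half-life or recovery time.
- That the illustrated Week 12 row conceals a child above 60 msec. A child last dosed on Day 64 has no on-treatment Week 12 value to conceal.
- That a Week 9 ECG row would hold stoppers alone. No ECG is scheduled at Week 9, so no such row is planned.

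**Conclusion.** The point holds as an unresolved contradiction with a missing on-treatment limit. It should be corrected before the tables are programmed. The exposure is 147 of 336 possible last-dose days (138 if every borderline scheduled visit was held early) under 6.8.1, and none under 6.8.

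The larger count rests on three assumptions: 6.8.1 prevails, EOS is classed as early termination, and a stopper does not attend a scheduled visit whose target day is after the last dose. If such a visit were attended, its result would itself be off drug, with still no rule to separate it. The percentages describe the calendar. How many children stop, and when, is unknown.

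In the assumed example the mean moves by 5 msec (+20 to +15) and the count above 60 msec does not change. The direction depends on the off-drug value being lower than the others. If EOS were instead shown as its own nominal visit, that row would mix children still on drug through another supply with children about 3 weeks off drug.

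**What to change.** Replace the conflicting text in SAP 6.8 and 6.8.1 with one rule:

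1. By-visit ECG, laboratory and vital-sign displays use only assessments up to last dose date + 1 day, the convention already in SAP 6.7.7.4.
2. Later assessments go to a separate post-treatment follow-up row added to Table 4.
3. EOS assessments done on drug by children moving to another supply stay in their scheduled week.
4. State whether EOS counts as a scheduled or an early termination visit, and whether an on-treatment unscheduled or early termination result may fill an empty window.
5. Leave the worst-post-baseline rules unchanged.

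The cost is one derived on/off-treatment flag, one table row and some wording. No new data are needed.

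Separately, the sponsor should reconcile Protocol 7.3.1, 9.5.3 and 9.6 on which visit applies to a child who stops in Part 1 or Part 2. No added visit is proposed here, and the SAP change does not depend on the answer.
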